At the clinic, patient will meet face to face with a person that is authorized to discuss and document consent (see "person designed to discuss and document consent"). After patient reads the consent the clinician will go over the consent with the patient and answer all the patient's questions. After answering all the patient's questions by the clinician patient will sign the study consent. The highest educational degree needed for the consenting clinician is a Doctor of Medicine degree (M.D.). Throughout this process, the patient will be told that they are free to refuse to participate in the research and that participation or non participation in research has no effect on their ability to continue to receive clinical care or services.

Indicate which of the following are employed as a part of screening or main study consent procedures

✓ Consent Form

Persons designated to discuss and document consent

Select the names of persons designated to obtain consent/assent

[name], MD

[name], MD

[name], MD

Type in the name(s) not found in the above list

Study Procedures

Describe the procedures required for this study

The study consists of the following procedures: 1) screening and diagnostic assessments including: psychiatric interview and medical history, SCID interview, labs and urine drug screen, informed screening consent (3 hrs.); 2) informed study consent, baseline fMRI, behavioral task (2 hours); 3) Ten treatment visits and self-report forms, including CGI (1.5 hours); 4) Midpoint clinical assessment after treatment visit 5 and self-report forms (1 hour) ; 5) Follow up clinical assessment, follow up fMRI and behavioral task (2.5 hours); and 6) 3 month follow up clinical assessment and self-report forms.

4.A1. Preliminary Screening: Potential subjects will be screened by telephone by a research assistant after obtaining oral consent as a part of the Anxiety Disorders Clinic's preexisting screening protocol (IRB #7094R). Patients on prohibited psychoactive medication will be excluded and will not be tapered off such

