cartoon face. The task includes three blocks of 100 trials. The difference between mouth sizes presented as well as the duration of stimulus exposure (100ms) is small, providing a setting in which a response bias may develop in response to asymmetric reinforcement: either the short or long mouth is rewarded (“Correct!! You won 20 Cents”) three times more frequently (“rich stimulus”) than correct identification of the other mouth (“lean stimulus”). In each block, only 40 correct trials (30 rich, 10 lean) are rewarded, so each subject is exposed to the same reward ratio. Subjects are informed that the purpose of this task is to win as much money as possible. Moreover, they are instructed that not all correct response will receive a reward feedback but they will be unaware that one of the stimuli will be disproportionately rewarded. Performance will be analyzed with respect to response bias, discriminability, and reaction time (RT), following prior procedures. This task will take approximately 25 minutes.

Attention Allocation Task: In each trial subjects will be shown a stimuli matrix containing 16 images, 6 negative and 6 neutral, for 6 seconds. The task is comprised of two 30 trial blocks. Participants will be asked to view the different image matrices freely with no specific instructions while being recorded by an eye-tracking apparatus collecting eye-movement data. Eye-tracking recording does not pose any danger or harm for participants. The task will take approximately 20 minutes.

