Pramipexole. In addition to receiving PE as described above, patients will have Pramipexole treatment administered by our team’s psychiatrists who have expertise in PTSD pharmacotherapy and clinical trials. Initial dosing will follow the methods of [name] (Preliminary Studies 3.3.B.6) and Goldberg (13): Daily dose will be started at 0.25 mg/day and increased by 0.25 mg/day every 3-4 days to a target of 2.5mg day by week 5. Beginning week 6 daily dose will be increased weekly by 0.5 mg/day to a maximum dose of 4mg. Adverse events will be systemically queried at each visit and vital signs will be checked. Compliance will be assessed by weekly pill count. Dose will be increased as tolerated unless the patient has achieved remission and will be decreased in the event of intolerable adverse events. Patients will check in with their treating psychiatrist for 15 minutes after every PE treatment session, for a total of 10 visits, normally conducted once a week (note—make up for missed sessions are allowed within 10-12 week time frame). Patients will see the same psychiatrist for each of their treatment visits. Staff psychiatrists carry beepers or cell phones and are available 24 hours per day for clinical emergencies. Patients will receive written information on how to contact staff by telephone or pager in the event of an emergency.

4.A.4. Midpoint Assessment (week 5): Patients will meet with a clinician and complete CAPS-V, HRSD-17,

CGI, CVC Suicide Risk Assessment and Screener and TBI performed by trained research team member and self-report forms: PCL-5, BDI-II and SHAPS.

4.A.5. Follow up visit: Patients will repeat fMRI scanning session and behavioral tasks. Procedures are identical to the first fMRI session. Follow up medical examinations, including physical exam, blood work, urinalysis will not be done routinely, but will be performed at any time during the study if clinically indicated by occurrence of a specific adverse effect. In addition, patients will complete a follow up assessment with a CAPS-V, HRSD-17, CVC Suicide Risk Assessment and Screener and CGI performed by trained research team member; and self-report forms: PCL-5, BDI-II and SHAPS.

4.A.6. 3 Month follow up visit: Patients will meet with a clinician and complete CAPS-V, HRSD-17, CGI and TBI performed by trained research team member and self-report forms: PCL-5, BDI-II and SHAPS.

You can upload charts or diagrams if any

Criteria for Early Discontinuation

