Study participants will receive \$100.00 for the completing the first MRI visit (\$16.20 for completion of the Probabilistic Reward Task, \$20 for completion of the self-report tasks and \$63.80 for completion of the MRI), \$100 for completing the second MRI visit (\$16.20 for the Probabilistic Reward Task \$20 for completion of the self-report tasks and \$63.80 for completion for the MRI). Participants will receive 30\$

for completion of the midpoint evaluation (clinician assessment and self-report forms). Participants will also receive an additional \$50 for completing the 3-month follow up (clinician assessment and self-report forms). Study patients will receive up to a total of \$280 for their participation in the study. Compensation will be pro-rated if the subject does not complete all the study procedures. Payments to subjects will be in the form of a check payable by RFMH mailed to the participant within 4-6 weeks of the end of the subject's study participation.

References

References

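### Does the Probabilistic Reward Task need a stated rich-mouth rule for each session before its pre-post change can be used?

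*Combined protocol and SAP*

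**What the plan says.** The Lay Summary describes one group of 15 adults, all receiving Prolonged Exposure plus pramipexole, with the PRT and an attention task at baseline and post-treatment. Study Procedures lists "informed study consent, baseline fMRI, behavioral task (2 hours") at the start and "Follow up clinical assessment, follow up fMRI and behavioral task (2.5 hours") at the end. Section 4.A.5 repeats this: "Patients will repeat fMRI scanning session and behavioral tasks". The sentence after it describes the procedures as the same as in the first scanning session. Compensation and/or Reimbursement pays for the task at both MRI visits: $"16.20 for completion of the Probabilistic Reward Task" at the first and $"16.20 for the Probabilistic Reward Task" at the second.

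Only one form of the task is described: a short (11.5 mm) or long (13 mm) mouth shown for 100 ms, in three blocks of 100 trials, with 30 rich and 10 lean rewards per block. On the rich stimulus the text says "either the short or long mouth is rewarded" three times as often as the other. Subjects are told that not every correct response earns a reward, but "they will be unaware that one of the stimuli will be disproportionately rewarded". On analysis: "Performance will be analyzed with respect to response bias, discriminability, and reaction time (RT), following prior procedures".

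The documents do not say how the rich mouth is assigned to a patient, or whether it is kept, switched or redrawn at the second session.

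**The concern.** The task measures a bias that is learned during the session, and its description relies on patients not knowing that the rewards are unequal. By the second session they have already been through it once. If a preference for the baseline rich mouth survives, it adds to the post-treatment response bias when the same mouth is rich again and subtracts from it when the mouth is switched. With one arm, either shift is mixed with the treatment effect, and the text does not let a reader work out even its direction.

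The reference to prior procedures does not settle this, because it is attached to how performance is analyzed. Reward processing is central to the rationale for pramipexole, and the Lay Summary says the pilot is meant to supply preliminary data for a grant application. A PRT change carried forward from this study could therefore look larger or smaller than it really is.

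**Working it through.** The plan gives no PRT test, standard deviation, effect size or carry-over size, so there is no planned figure to reproduce. What can be done is to check the task's own numbers and then see how far an assumed carry-over would move a simple pre-post test.

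**Task figures (Study Procedures).** 30/10 = 3, which agrees with the stated threefold ratio. 30 + 10 = 40 rewarded trials per block, which also agrees. Baseline exposure is 3 × 100 = 300 trials, with up to 3 × 30 = 90 rich and 3 × 10 = 30 lean rewards.

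**Assumptions for the sensitivity check (none is in the documents except n).** n = 15 completers (Description of Subject Population); one-sample t-test on the change score, two-sided 5%; stimulus-specific carry-over c of 0.1, 0.2 or 0.5 SD of the change score.

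- Critical value t(0.975, 14 df) = 2.145. The 95% half-width is 2.145/√15 = 0.554 SD.
- c as a share of the half-width: 0.1/0.554 = 18%, 0.2/0.554 = 36%, 0.5/0.554 = 90%.

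**Case 1: the same rule for every patient.** The mean change shifts by +c if all keep the mouth and by −c if all switch. The chance of a significant result in the direction of the shift comes from the noncentral t distribution with noncentrality m√15, where m is true change plus carry-over.

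| Setting | No carry-over | c = 0.1 | c = 0.2 | c = 0.5 |
|---|---|---|---|---|
| No true change: false rise (all kept) or false fall (all switched) | 2.5% | 5.5% | 10.8% | 43.8% |
| True rise of 0.5 SD, all kept: chance of detecting it | 43.8% | 58.0% (m = 0.6) | 71.3% (m = 0.7) | not run |
| True rise of 0.5 SD, all switched: chance of detecting it | 43.8% | 30.3% (m = 0.4) | 19.0% (m = 0.3) | not run |

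**Case 2: the rich mouth is drawn independently at each session.** The wording of the task description allows this just as well. Each patient keeps the mouth with probability 1/2 and is switched with probability 1/2, so the expected shift is ½(+c) + ½(−c) = 0. The spread of the change score grows slightly, to √(1 + c²) = 1.005, 1.020 and 1.118 SD. In a simulation of 400,000 trials of 15 patients per setting, with no true change, the false-rise and false-fall rates were each about 2.5% at all three values of c. With a true rise of 0.5 SD, detection was 43.4%, 42.3% and 36.2% for c = 0.1, 0.2 and 0.5, against 43.8% without carry-over. The cost in this case is a little precision and no systematic error.

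The size of the problem therefore depends on two unknowns, the carry-over itself and the assignment rule, and it runs from nil to serious over the assumed range. The 43.8% false-positive figure needs both a uniform rule and the top of that range, with the bias lasting across a treatment period of 10 to 12 weeks after a task of about 25 minutes.

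**What the analysis needs in any case.** Response bias is a preference for the more-rewarded mouth, so it cannot be scored unless the rich mouth is known for that patient and session. Anyone who computes the planned outcome must already hold the information that the text omits.

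**The case for a change.** The strongest case for acting is that the gap is real and a remedy is cheap. Neither nearby sentence closes it. The one that calls the follow-up procedures the same refers to the scanning session; even if it extends to the behavioral tasks, it could mean the same rich mouth or the same task with a fresh assignment, and the first keeps a carry-over of fixed sign while the second averages it out. One sentence in the protocol would settle the question, and in a one-arm study the reader has nothing else to lean on.

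The ambiguity stands. What does not stand is that the plan is wrong or that an inference depends on it. Only one task version is described, and the natural reading is that this version is repeated, so there is no doubt about the version. Stating the rule would tell a reader which way any carry-over runs, but it would leave the carry-over in place. Practice effects and awareness of the unequal rewards, which do not depend on which mouth is rich, would also remain. They come from having no comparator, an accepted limit of a small open pilot. The document is an institutional protocol summary form, and a task setting of this kind may well be held in the task materials.

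**Conclusion.** No change is needed. The text omits the rich-mouth assignment at each session, but this is missing detail and no evidence of a faulty task setting. The stated hypotheses concern PTSD symptoms, depressive symptoms and functional connectivity; the PRT is not among them, and the target of 15 completers does not rest on it. Response bias is also one of three PRT measures, with no priority given among them.

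The possible distortion ranges from no expected shift (mouth redrawn at each session) to ±c (one rule for all patients), with c unknown. The percentages above rest on an assumed c of 0.1 to 0.5 SD, 15 completers and a t-test that the plan does not specify. They show sensitivity and do not estimate the bias in this trial. When the PRT change is reported, an analyst would ordinarily give the rich mouth used at each session and name retest effects as a limitation; both can be done without amending the plan.

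A separate clerical slip sits in the next paragraph of the protocol: the attention task's matrix is said to hold 16 images, but the listed types add to 6 + 6 = 12. It has no bearing on the PRT.

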Criteria for Early Discontinuation

At least weekly, the PI and study psychiatrist will review participants awaiting study procedures and will withdraw a person from the study if the participant:

1. Requests to be withdrawn from the study.
2. Reports significant suicidal ideation, as assessed by the clinician and/or by the BDI-II suicide item > 2
3. Symptomatic worsening, as measured by a score of 6 (much worse) or 7 (very much worse) on the CGI at any visit, or as per the treating psychiatrist's judgment
4. Is non-compliant with protocol requirements.
5. Manifests a new or inter-current illness that prevents the patient from complying with the protocol

Blood and other Biological Samples

Please create or insert a table describing the proposed collection of blood or other biological specimens
20 cc of blood will be drawn for chemistry, CBC, and thyroid function tests.

Assessment Instruments

Create a table or give a brief description of the instruments that will be used for assessment

Structured Clinical Interview for DSM-V (SCID) (60 minutes at screening)

Clinician Administered PTSD Scale (CAPS-5) (30 Minutes)

Hamilton Rating Scale for Depression (HRSD-17) (10 minutes)

Posttraumatic Stress Disorder Checklist (PCL-5) (5 minutes)

Structured Pill Count Interview (5 minutes)

Treatment Emergent Side Effect Scale (10 minutes)
Life Events Checklist (LEC) (5 minutes)
Clinical Global Impression Severity and Improvement (CGI) (5 minutes)
Snaith-Hamilton Pleasure Scale (SHAPS) (5 minutes)
Traumatic Brain Injury Identification Method (TBI) (5 minutes)
CVC Suicide Risk Assessment and Screener (10 minutes)
Please attach copies, unless standard instruments are used

Off label and investigational use of drugs/devices

Choose from the following that will be applicable to your study

✓ Drug

Select the number of drugs used in this study

1

Drug #1

Name of the drug

Pramipexole

Manufacturer and other information

Generic brands will be used and therefore will be made by multiple companies.

Approval Status

No IND is required

Choose one of the following options

FDA has determined that IND is not required

Research Related Delay to Treatment

Will research procedures result in a delay to treatment?

Yes

Maximum duration of delay to any treatment

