- a) Pramipexole will be initiated conservatively following procedures of [name] and Goldberg (3) prior studies of depressed patients that resulted in low levels of adverse events. Daily dose will be started at 0.25 mg/day and increased by 0.25 mg/day every 3-4 days to a target of 2.5mg day by week 5. Beginning week 6 daily dose will be increased weekly by 0.5 mg/day to a maximum dose of 4mg. Dosage will be lowered or medication stopped if needed for adverse reactions. Patients will be carefully monitored for signs of daytime drowsiness and warned not to drive while drowsy if this occurs. Adverse events will be inquired about systematically through use of a checklist of side effects previously associated with pramipexole treatment, and vital signs will be assessed at each treatment visit.
- b) Patients will be educated about potential adverse interactions with other medications they may wish to take and advised to contact study physicians before starting new medications.
- c) Careful monitoring of patients weekly during study treatment by experienced clinicians. Patients will see the same clinician for each of their treatment visits. Staff psychiatrists carry beepers or cell phones and are available 24 hours per day for clinical emergencies. Patients will receive written information on how to contact staff by telephone or pager in the event of an emergency. In the event of clinically significant suicidal ideation or a medical or psychiatric emergency in the clinic, patients will be escorted to the emergency room of New York Presbyterian Medical Center, which is adjacent to New York State Psychiatric Institute.
- d) Patients will be instructed to contact study personnel during treatment in the event of worsening of symptoms or significant adverse events. Patients who experience clinically significant worsening (CGI change score > 5) will have study treatment discontinued and will be given appropriate clinical care until stabilized. All patients leaving study treatment will be offered 6 months of free open treatment, after which time they will be referred to appropriate clinical treatment.

- e) Patients will be consented prior to the start of study treatment, and they will be informed that they may withdraw from study treatment at any time.
- f) At the conclusion of study treatment patients discontinuing pramipexole will have it discontinued gradually under supervision.

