- g) At the termination of PE/pramipexole treatment, patients will be offered six months of open treatment, including the option to continue PE and/or pramipexole, or to receive other therapy or medication treatments, if clinically indicated.

MRI Scan: Subjects will be screened by interview and questionnaire to determine the presence or absence of metallic objects, and informed that they cannot participate in the study if their body contains any paramagnetic metal other than standard dental work. Earplugs will be provided to reduce discomfort. Staff will be available for help and support and, if the subject requests, the scan will be stopped. Women of child-bearing age will be required to have a pregnancy blood test at the time of medical screening and a pregnancy urine test on the day of the MRI scan. For women of child-bearing age, it will also be asked and it will be documented that they responded negatively (or procedure will not occur) to questioning on the MRI day (before the procedure is initiated) whether it is possible they may have become pregnant in the prior two-week period.

Prolonged Exposure treatment: Every effort will be made to insure patients' comfort during treatment, and patients will be withdrawn if needed.

Interviews/assessments: Subjects will be informed that they may choose not to answer specific questions, and may stop the interview at any time if they are feeling uncomfortable. Every effort will be made to insure patients' comfort.

All patients will be assessed using the Columbia Veterans Center Suicide Risk Assessment and Screener instrument at intake, midpoint, and termination. Patients will also be continuously assessed by treating clinicians and by means of the BDI-II.

In the case of clinical deterioration or evidence of suicide risk, the on-call psychiatrist will be involved and available to see the patient right away and supervise the patient's management in the event of a serious problem such as worsening of suicidal ideation. In the occurrence of active suicidal ideation, the participant will be removed from research and be treated as clinically indicated.

For those deemed to be at greater than minimal risk at any time, the following steps will be taken:

- Provision of contact information for emergency services (911, Anxiety Disorders Clinic pager, NYC Mobile Crisis Team)
- Scheduling with ADC MD as soon as possible
- Completion of Safety Plan, copy of which is kept by patient

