- Discussion of removal of means, including firearms
- Increased frequency of visits
- Phone check ins between sessions and upon missed appointment

For those at high risk, the following will be considered based on clinical judgment:

- Referral to high risk treatment program, such as DBT

- Emergency room (voluntary)
- Emergency room (involuntary)

For those who present with elevated risk at termination, we will offer:

- Referral to alternate or high risk treatment programs, as indicated

Blood-drawing: Proper sterile techniques will minimize the rare risk of infection.

Audiotaping: The purpose of the audiotaping will be explained, confidentiality will be respected, and tapes will be erased after the spot checks or following supervision. Informed consent for taping will be obtained.

Other Procedures for Minimizing Risk:

- 1) Careful medical and psychiatric screening to identify patients for whom risk for potential adverse effects are elevated. Such patients will be excluded from the study. As an example, an actively suicidal patient would be excluded from study participation and appropriate clinical treatment provided.
- 2) Patients with any of the following will be removed from research and treated openly or as clinically indicated: a) the occurrence of assaultive or illegal behavior; b) the occurrence of active suicidal ideation at any point during the trial as assessed by clinical interview; c) behaviors while intoxicated that are a danger to him/herself or others.
- 3) Inclusion of psychoeducation about PTSD, the treatment process and memory triggers within the therapeutic framework.
- 4) Careful monitoring of patients during pretreatment and study participation by experienced clinicians. Patients will see the same clinicians for each of their treatment visits.
- 5) Ability to remove any patient from the study who evidences significant clinical deterioration during acute treatment. Provisions will be made for appropriate clinical care of such patients.
- 6) Patients failing to benefit from the study treatment will be exited from the study and provided with appropriate clinical care based on weekly review with termination criteria (see section 4A.7).
- 7) All data will be coded and stored in locked files to insure confidentiality.

Methods to Protect Confidentiality

Describe methods to protect confidentiality

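### Suicidal ideation removes a patient from the study, the rules for CGI worsening conflict, and no CAPS-5 or HRSD-17 is scheduled at or after exit, so endpoint scores would be lost mainly from patients doing badly

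*Combined protocol and SAP*

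**What the plan says.** **Suicidal ideation.** Three places agree.
- Criteria for Early Discontinuation says the team "will review participants awaiting study procedures and will withdraw a person from the study if the participant" meets a listed criterion. Item 2 is: "Reports significant suicidal ideation, as assessed by the clinician and/or by the BDI-II suicide item > 2".
- The Interviews/assessments paragraph of the risk-minimisation section says: "In the occurrence of active suicidal ideation, the participant will be removed from research and be treated as clinically indicated".
- Other Procedures for Minimizing Risk, item 2, says: "Patients with any of the following will be removed from research and treated openly or as clinically indicated". Its part (b) is "the occurrence of active suicidal ideation at any point during the trial as assessed by clinical interview".

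**CGI worsening.** The places do not agree.
- Criteria for Early Discontinuation, item 3, withdraws the patient from the study for: "Symptomatic worsening, as measured by a score of 6 (much worse) or 7 (very much worse) on the CGI at any visit". The treating psychiatrist's judgement is an alternative trigger.
- Minimizing risks of pramipexole, item d, says: "Patients who experience clinically significant worsening (CGI change score > 5) will have study treatment discontinued". It does not mention leaving the study.
- Other Procedures for Minimizing Risk, item 5, gives only the ability to remove a deteriorating patient, which is discretionary.

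**Ratings.** After baseline, CAPS-5 and HRSD-17 are scheduled at week 5 (4.A.4), post-treatment (4.A.5) and 3 months (4.A.6). No section schedules either scale at early exit or keeps removed patients in these visits. The instrument named for termination is the suicide-risk screener. BDI-II is completed at every therapy session (4.A.3), and CGI is listed among the treatment-visit forms (Study Procedures).

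**Sample.** Description of Subject Population gives 15 completers needed and 20 enrolled. No analysis set, test or missing-data method is stated.

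**The concern.** The hypothesis is that PTSD and depressive symptoms improve. Suicidality and global worsening are closely related to those symptoms. A rule that ends study participation on these events makes the CAPS-5 and HRSD-17 endpoints missing for reasons tied to the outcome. A patient removed before week 5 would have only baseline values on both scales.

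The study has one arm, so no comparison group with similar losses offsets the effect. Its stated purpose is to give preliminary feasibility, safety and efficacy data for a grant application, and an inflated pre-post change would carry into that application. Ratings not taken at exit cannot be recovered later. Separately, staff who see a CGI of 6 have two different instructions.

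**Working it through.** **1. The plan's own figure.** 15 completers of 20 enrolled implies (20 − 15)/20 = 25% non-completion, and 15/(1 − 0.25) = 20. The figures are consistent, but the 25% is back-calculated because no dropout rate is stated. At most 5 projected non-completers could leave through these triggers. The documents do not say how many would, so I take k = 0 to 5.

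**2. Shift in the completers' mean.** Assumptions, none from the documents: 20 patients; normally distributed change scores with SD 1, higher meaning better; the k patients worst on a trigger index leave; the index has correlation ρ with final change. Then

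shift = ρ × m_k,

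where m_k is the expected mean of the best 20 − k of 20 standard normal values. Simulation gives m_k = 0.098, 0.181, 0.258, 0.332 and 0.404 for k = 1 to 5. For k = 5, 0.5 × 0.404 = 0.20 and 0.7 × 0.404 = 0.28. Simulating each ρ directly gives:

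| Removed (k) | ρ = 0.3 | ρ = 0.5 | ρ = 0.7 |
|---|---|---|---|
| 0 | 0 | 0 | 0 |
| 1 | 0.030 | 0.050 | 0.068 |
| 2 | 0.055 | 0.092 | 0.126 |
| 3 | 0.078 | 0.130 | 0.180 |
| 4 | 0.100 | 0.167 | 0.232 |
| 5 | 0.122 | 0.203 | 0.282 |

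Entries are in SD of the change score, in the direction of apparent benefit.

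**3. What recorded data could recover.** BDI-II and CGI are collected during treatment, including before week 5, so the trigger itself is largely on record. In the same model with k = 5 and ρ = 0.5, I predicted the missing final scores by regressing final change on the recorded trigger in completers:
- trigger recorded exactly: bias falls from 0.20 to 0.00 SD;
- trigger recorded in 8 levels: 0.01 SD;
- trigger recorded with reliability 0.7 (assumed): 0.09 SD.

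The fall to zero follows from the model, in which removal depends on the trigger alone. Real removals also involve clinical judgement, so some bias may remain.

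**4. Cost of continued ratings.** The times come from Assessment Instruments; BDI-II is not timed there.
- Week 5: CAPS-5 30 + HRSD-17 10 + CGI 5 + suicide screener 10 + TBI 5 + PCL-5 5 + SHAPS 5 = 70 min
- Post-treatment: 30 + 10 + 10 + 5 + 5 + 5 = 65 min (no TBI)
- 3 months: 30 + 10 + 5 + 5 + 5 + 5 = 60 min (no suicide screener)
- Five patients removed before week 5: 5 × (70 + 65 + 60) = 975 min = 16.25 h
- Exit rating (CAPS-5, HRSD-17, CGI): 5 × (30 + 10 + 5) = 225 min = 3.75 h
- Total: 16.25 + 3.75 = 20 h at most
- Payments at the stated rates (midpoint $30, post-treatment self-report $20, 3-month $50): 5 × $100 = $500 at most

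**The case against.** **Scope of the withdrawal rule.** The lead-in to Criteria for Early Discontinuation concerns participants awaiting procedures. It could be meant for the wait of up to two weeks before treatment. Item 3 applies at any visit, and item 2(b) of Other Procedures for Minimizing Risk applies throughout the trial, so the narrow reading fails for ideation. For CGI worsening part of the objection stands: a reader might infer that worsening always ends study participation, but item d stops only treatment and item 5 is discretionary. Other Procedures item 6 also exits patients who do not benefit, but refers to termination criteria that do not list non-benefit. It is at most an unclear extra trigger.

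**Numbers affected.** Zero removals is possible. Entry criteria exclude patients at suicide risk, and patients may leave for other reasons such as request, non-compliance or illness. The real triggers are also absolute thresholds, whereas the model ranks patients. This stands, which is why the range starts at zero.

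**Existing data.** A reader might infer that only week-5 ratings can fill the gap. The session BDI-II and CGI show otherwise. They still do not measure CAPS-5, and they are not scheduled after the patient leaves.

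**False-positive rates.** A reader might turn the shift into an inflated type I error. The documents name no test or alpha, and this is a pilot, so they do not support such a figure. Nor do they say that completers alone will be analysed; the 15 completers are a recruitment target.

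**Safety and comparability.** Ending research contact with an actively suicidal patient is a defensible clinical choice, and later ratings may reflect open treatment. Both points limit the fix, but neither argues against an exit rating where it is safe.

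**Conclusion.** The concern holds in a limited form. Removal from the study or from research for suicidal ideation is a stated rule. For CGI worsening the text contradicts itself and needs reconciling. In neither case is CAPS-5 or HRSD-17 scheduled at or after exit, so following the plan would lose endpoint scores for outcome-related reasons.

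The effect on a completers-only mean lies between 0 and about 0.28 SD. That range rests on 0 to 5 removals of 20, a trigger-outcome correlation of 0.3 to 0.7, normal change scores, and the inference that completers are what would be summarised. Using the recorded BDI-II and CGI could remove much of it. Because the gap is cheap to close before it occurs and cannot be closed afterwards, the sponsor should act. Confidence is medium, since the number affected is unknown.

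**What to change.** Keep every safety trigger.

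1. Align Criteria for Early Discontinuation items 2 and 3, the ideation sentence under Interviews/assessments, and Other Procedures for Minimizing Risk item 2(b) with item d of the pramipexole section: study treatment is stopped and the patient is treated as clinically indicated.
2. Add a CAPS-5, HRSD-17 and CGI at exit where safe. Continue the clinical ratings in 4.A.4 to 4.A.6, timed from treatment start and without scans or tasks, unless the patient declines or the clinician judges them unsafe.
3. Report change in all patients who start treatment, using all available ratings including session BDI-II and CGI, alongside the completers. Note any treatment received after stopping.
4. List each removal for suicidality or worsening as a safety outcome.

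The cost is an amendment and consent wording, plus at most about 20 rater hours and $500. The main downside is that ratings after exit may reflect open treatment, so the exit rating is the most interpretable.
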